12) To answer the secondary research questions, starting in the second month after implementation, study manager will carry out **in-depth interviews** (or small focus group discussions) with providers at sites in both study groups. We will interview providers who use the paper partograph or the ePartogram to discuss barriers and facilitators to usage, including facility conditions. The supervision for providers around the ePartogram and paper-partograph use will also be explored. The interviews will be audio-recorded to capture all contributions from participants. Participants will be informed about this during consenting. The digital recorders erased/audio tapes will be destroyed after transcription and the recordings will not be used for any other purposes.

B. Provide a **sample size and a justification** as to how you arrived at that number. If you use screening procedures to arrive at a final sample a table may be helpful.

The third study objective deals with clinical actions for complications and requires the largest sample size due to the rarity of complications. We describe inputs to sample size as shown in Table 1.

Inputs to the sample size calculation are as follows:

- *Number of sites*: The available 12 sites (6 in each study arm) have 1342 births per month, , on average. So 6 facilities have 671 births per month. We believe 80% of these will have a partograph completed during the study.
- *Prevalence*: Kenya QoC report⁹ stated that “19% of labors crossed the partograph ‘action line’”. While this appears high, we also will look for labors with more than one abnormal measurement signaling an early complication. (A study by Orji et al in Nigeria in 2008 also found 18.5% of labors crossed the action line.) For our study, we use the 19% to indicate that up to 19% of labor may cross the action line OR may have 1+ abnormal measurement that signal need for provider action.
- *Average cluster size*: is calculated to be 17.6
- *Intraclass correlation*: ICC is expected to be high as the facilities are a heterogeneous mix of district hospitals, health centers and some private facilities, so we assume ICC of 0.15.
- *Coefficient of variation*: COV is assumed to be 90%, after calculating the standard deviation of the average monthly births in these sites. Therefore, the design effect is high at 5.3, calculated as follows: $1 + ((\text{average cluster size } 16.4 - 1) * (1 + (\text{COV } 0.80^2)) * \text{ICC } 0.15)$.

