In the exercise of completing the Health Worker Line Listing at each facility, we will document the numbers of cadres (Kenya Enrolled Community Health Nurses; Kenya Registered Community Health Nurses; Kenya Registered Nurses; Kenya Registered Nurse Midwives and Bachelor of Science in Nursing Nurses) and doctors (ObGyn and medical officers). A purposive sample of all cadres using the ePartogram or partograph will be selected. At high-volume sites, a sample of half of the providers on duty in a month and half of the supervisors will be interviewed. At lower-volume sites: all providers and supervisors will be interviewed. We will also interview each facility in-charge and district authority. So there are 4 respondent types: providers, supervisors, facility-in-charge and district authority.

The study staff will carry out the interviews when visiting the facility starting in second month. Each facility will have qualitative data collected at one point in time.

For the qualitative data, we will select 8 busy facilities: assume 2 to 8 providers per site (average 4 providers), $8*4 = 32$. One supervisor from each site: 8. Up to 4 in-charges and 4 district authorities. **Total 48 participants**. Note these qualitative participants will be part of the larger group of participants who consent to be part of the in the overall study.

IV. Participants

Describe the study participants and the population from which they will be drawn. Specify the inclusion and exclusion criteria. If you plan to include children, note their ages and whether you will include children in foster care. Note if the participants are particularly vulnerable in terms of cognitive limitations, education, legal migration status, incarceration, poverty, or some combination of factors.

Facilities

The facilities will include the higher referral-level hospitals in Kisumu and Meru, as well as lower level hospitals. The facilities will include both BEmONC and CEmONC sites.

Facility Inclusion Criteria:

- In Kisumu or Meru
- BEmONC or CEmONC sites
- At least one SBA on duty in labor ward 24 hours per day
- Facility in-charge or in-charge of L&D ward available physically or remotely 24 hours per day
- Use WHO modified paper partograph
- Adequate supply of paper partographs and maternity registers
- Availability of reliable transportation for referrals (e.g. functional ambulance or other) 24 hours per day

Facility Exclusion Criteria:

- Facility not registered with MOH

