P2. Decision-making and actions taken to maintain normal labor (Tool 4)	Data on each partograph parameter will be entered for each time period, as well as actions taken in labor. Jhpiego clinical rules will be applied to the data in the extraction database to determine appropriate clinical actions for a labor without any complication. This is a binary variable.	Labors in which Section 3 marked as “Normal Labor”	First, we will examine the frequency/prevalence of each clinical action taken in normal labor and compare between the two study groups. Second, we will carry out same analysis as for Objective P1.
P3. Detection, decision-making and action to address deviations from normal labor and complications arising during labor—for ‘slow’ labor, prolonged labor, obstructed labor and cephalo-pelvic disproportion	Data on each partograph parameter will be entered for each time period, as well as actions taken in labor. Jhpiego clinical rules will be applied to the data in the extraction database to determine appropriate clinical actions for a labor with a specific complication. This is a binary variable.	Labors in which Section 3 marked “Slow labor, prolonged labor, obstructed labor or cephalo-pelvic disproportion”	First, we will examine the frequency/prevalence of each clinical action taken in selected complications and compare between the two study groups. Second, we will carry out same analysis as for Objective P1.
-- for all complications (Tool 4)	Same as above. A composite variable will be created for all complications. This is a binary variable.	Labors in which Section 3 marked as ANY complication	First, we will examine the frequency/prevalence of each clinical action taken in all

			complications and compare between the two study groups. Second, we will carry out same analysis as for Objective P1.
S1. Is facility use of ePartogram (vs. paper-partograph) associated with lower rate of...?			
From the Register Analysis			
Neonatal deaths <24 hours and (Tool 5)	Number of early neonatal deaths. This is a count variable.	All live births	We will compare means using t-tests across 2 groups. Next, we will use unadjusted regression models that account for clustering (correlation) of data within the facility. Poisson regression with offset term (or another appropriate model to be explored) will be used for bivariate and multivariable analysis.

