Intrapartum death (fresh stillbirth rate) (Tool 5)	Number of fresh stillbirths. This is a count variable.	All live births	Same as above.
Adverse perinatal events (Neonatal deaths <24 hours+ intrapartum death (fresh stillbirth rate))	Number of neonatal deaths and fresh stillbirths	All live births	Same as above.

Statistical analysis plan

Outcomes will be dichotomous, yes/no for each measure.

In the main statistical analysis of our primary outcomes, we will focus on program effect (intervention (ePartogram) group of facilities versus comparison (paper program) group of facilities) as the main predictor of interest. The analysis will be performed at the level of the individual case (partogram). In preliminary analyses we will conduct univariable and bivariable analyses to assess the distribution of key variables and joint distributions and unadjusted relationships.

In final analyses addressing study aims, we will fit multi-level, multivariable regressions models for the outcomes with adjustment for possible confounders and account for clustering by provider and/or study clinic by the use of GEE.

While we have selected clinics roughly matched between the intervention and comparison regions, we will still evaluate confounding to attain the least biased estimate of our intervention effect. Facility level possible confounders are: monthly case load of laboring women, number of providers, key equipment availability etc. Provider-level possible confounders that may be adjusted for are years of work experience since graduation and cadre. Woman-level possible confounders are age and parity.

5. Describe whether you are collecting or storing **personal identifiers**, and if yes, why you need them, and when and how you plan to dispose of them. Signatures on consent forms are considered to be identifiers.

Identifiers of Providers

Our study will assign each facility and each provider a study id number of the Health Worker Line Listing form to be updated monthly. This will be kept separately from partograph data.

partograph review analysis: the paper partograph has a place for a provider to sign it. When we scan/photocopy paper partographs, we will obscure the provider name (cover with lose paper) but will we add/write on it the provider study id number.

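### Table 5 opens each S1 analysis with a t-test of means on a count outcome, with no denominator or unit stated, and does not name the offset model as the deciding analysis

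*Combined protocol and SAP*

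**What the plan says.** The S1 block of Table 5 (section V.C.4) asks: "Is facility use of ePartogram (vs. paper-partograph) associated with lower rate of" neonatal death within 24 hours, fresh stillbirth, and the two combined. The outcome column gives "Number of early neonatal deaths. This is a count variable" for the first row, "Number of fresh stillbirths. This is a count variable" for the second and "Number of neonatal deaths and fresh stillbirths" for the third. The cases column of each row reads "All live births".

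The analysis cell of the first row begins "We will compare means using t-tests across 2 groups". It then moves to unadjusted regression that allows for clustering within facility, and to Poisson regression with an offset (or some other model still to be explored) for bivariate and multivariable work. The other two rows refer back to that cell, so all three outcomes inherit both the t-test and the model.

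Three statements elsewhere bear on birth volume:

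- Section III.B: "COV is assumed to be 90%, after calculating the standard deviation of the average monthly births in these sites".
- Section IV: "The facilities will include the higher referral-level hospitals in Kisumu and Meru, as well as lower level hospitals".
- Section III.A, phase 2: assignment is purposive and aims for similar birth volume in the two groups as far as possible. Two named hospitals are fixed in the intervention group.

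**The concern.** A facility's expected number of deaths is its births multiplied by its risk. A t-test on numbers therefore answers the rate question only if births are comparable between arms. Even then, the spread in facility size goes into the error term. Here that spread is large, and assignment is purposive with two sites fixed.

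The cell also does not say whether the unit is the facility or the facility-month, although the register review tool records monthly figures. Nor does it say which of the listed steps decides S1. These are the study's only mortality outcomes and the results go to the Ministry of Health, so the first comparison should be one that can be interpreted.

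**Working it through.** The plan gives no event rate, power or sample size for S1, so there is no S1 figure to reproduce. The 1004 partographs per group in section III.B are for P3.

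**Inputs from the documents.** There are 12 facilities, 6 per arm, with 1342 births per month (671 per arm). The volume coefficient of variation (CV) is 0.90, as in the text and Table 1 of section III.B; the formula printed in the same bullet shows 0.80. Collection is expected to take 2 or 3 months; 3 is used here.

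**Assumptions, not in the documents.** 25 events per 1000 births (10 as the lower case), between-facility CV of the rate 0.25, lognormal volumes, Poisson counts given the rate, one total per facility, two-sided 5% test.

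**By hand, equal expected volume, rate halved.**

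- Births per facility: 1342/12 × 3 = 335.5. Expected events: 335.5 × 0.025 = 8.39 in control and 4.19 in intervention.
- Squared CV of a facility count = 1/mean + CV_vol² + CV_rate² + CV_vol² × CV_rate². For control this is 0.119 + 0.810 + 0.0625 + 0.051 = 1.042. Volume alone supplies 0.810/1.042 = 78% of it.
- Variances: 1.042 × 8.39² ≈ 73.3 (control) and (0.238 + 0.923) × 4.19² ≈ 20.4 (intervention). Standard error of the difference: √[(73.3 + 20.4)/6] = 3.95. Difference over standard error: 4.19/3.95 = 1.06.
- For facility rates, the variance is rate² × 0.0625 + rate × E(1/births), where E(1/births) = 1.81/335.5 = 0.0054 for lognormal volumes. This gives 0.000174 (control) and 0.000077 (intervention). Standard error: √(0.000251/6) = 0.0065. Difference over standard error: 0.0125/0.0065 = 1.93.

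The t critical value on 10 degrees of freedom is 2.23. The rate test has almost twice the signal of the count test on the same data.

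**Simulation on the same assumptions, percentage of trials rejecting.**

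| Setting | t-test on counts | t-test on facility rates |
|---|---|---|
| Equal risk, equal expected volume, 25/1000 | about 4 | about 4 |
| Equal risk, facilities paired on volume, 25/1000 | about 0.3 | about 4 |
| Rate ratio 0.5, equal expected volume, 25/1000 | about 15 | about 45 |
| Rate ratio 0.5, facilities paired on volume, 25/1000 | about 8 | about 45 |
| Rate ratio 0.5, equal expected volume, 10/1000 | about 13 | about 23 |
| Equal risk, intervention volume 2 times control, 25/1000 | about 16 | about 5 |
| Equal risk, intervention volume 3 times control, 25/1000 | about 34 | about 5 |

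**Point estimates.** A separate simulation used event risks of 1% and 3% and no between-facility variation in risk. With equal risk, the median ratio of mean counts was 1.0 when facilities were matched on volume. It was about 1.21 when the intervention arm held the larger of each of the two biggest pairs, and about 1.75 when it held the two largest sites and the rest were random. With a true rate ratio of 0.7 the corresponding values were 0.69 to 0.70, 0.85 and 1.21. The births-based ratio stayed at 0.69 to 0.71 throughout.

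**Unit.** If facility-months were the unit, which the plan neither says nor excludes, the count t-test would reject a true null in about 23% of trials at equal expected volume, because months from one facility are not independent.

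**The case against.** The best reply is that the cell already holds the remedy: the next sentences plan regression that accounts for facility clustering and a Poisson model with an offset. The closing Statistical analysis plan paragraphs of V.C.4 treat unadjusted relationships as preliminary and put the study aims in the final multivariable models, and they list monthly case load as a possible confounder. All of this stands, and it is the main reason the point is modest. It does not remove the point. Table 5 does not label the t-test as descriptive, the model is left open to replacement, and the offset variable is not named.

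The means could also be means of facility rates, since S1 speaks of a rate and the rows name live births. The text does not settle this. The neighbouring column says count, and a cases entry does not by itself make the test use births. A clarification is needed on either reading.

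A reader might infer more than the documents support:

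- *That S1 compares facility size instead of risk.* A mean count reflects both. With equal volume the ratio of mean counts is on target, and similar volume is what the assignment aims for.
- *That the test will raise false alarms of harm.* This needs a volume imbalance. No facility volumes are given, the ratios of 2 and 3 are assumptions, and nothing says the two fixed hospitals are the largest. With facilities paired on volume, the count t-test almost never rejects a true null; the loss is then in power.
- *That the test cannot detect a real reduction.* Its power is low, not zero.
- *That the report will carry two conflicting S1 conclusions.* The plan does not say the t-test will be reported as a conclusion. It only leaves the order of authority open.

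**Conclusion.** The point holds in limited form. As written, the first S1 comparison is a t-test of means on outcomes defined as counts, with no denominator or unit, while the question concerns a rate. On counts it is confounded with birth volume if the arms differ in volume. If they are balanced it gives up much of the available power: about 8% to 15% against about 45% at 25 per 1000 and a halved rate, with type I error of about 4% for both tests when facilities are not paired on volume.

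The volume CV, the number of facilities, the total births and the collection period come from the plan. The event rates, between-facility rate variation, effect size and volume imbalances are assumptions. At 10 per 1000 the power gap narrows to about 13% against 23%. S1 is secondary, no primary result depends on this sentence, and a suitable model is already in the cell. This is a modest correction, not a must-fix.

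**What to change.** In all three S1 rows of Table 5:

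1. Delete the t-test on counts, or state that it is run on facility rates (events divided by births) with one value per facility.
2. Show events, births and the rate for each of the 12 facilities.
3. Name the rate ratio from the facility-clustered Poisson or negative binomial model, with a log(births) offset, as the main S1 analysis.
4. Define the births used in the offset for each row. Live births fit the neonatal death row. Live births leave out stillbirths, so total births are the natural denominator for the other two rows.

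The register review tool (Tool 5, Table 4) already abstracts deliveries, live births and stillbirths. The cost is a few words in Table 5 and no extra data collection.

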While study results demonstrated many benefits of ePartogram use, additional needed software refinements were identified, and further research is needed to assess its use in a greater variety of clinical settings. The proposed ePartogram effectiveness aims to further test the ePartogram software and use of ePartogram on clinical decision-making and care.

[figure not shown]
III. Study Design

- A. Provide an overview of your **study design and methods**.

Study Design

The study design is a quasi-experimental design evaluation with labor management outcomes compared for the study period between two study groups, intervention and control. The study will involve mixed methods – quantitative and qualitative data. The study is depicted below.

Figure 1. Study Design and Phases

Methods

The study will be conducted in the following phases.

Phases

- 1) An initial group of **facilities selected** for participation will be confirmed in Kisumu County and Meru County. A rapid formative assessment of possible facilities collected data on:
 - a. training needs on the paper partograph and
 - b. supplies, drugs and equipment available in stock for monitoring of normal labor, management of complications and referrals (facility assessment tool; this will be repeated every 3 months) (?).
 - c. percent of births recorded in the register at the facility in past 3 months that had a partograph started and used.
 - d. this activity received a non-HSR determination.
- 2) In each region, we expect approximately 6 facilities to participate. Within each region, equal numbers of facilities that will be purposively assigned to the study groups. Each study group will have facilities that have a similar birth volume, staffing levels, and BEmONC/CEmONC status, as much as possible so the two group are similar
 - a. Kisumu District Hospital and Meru Teaching and Referral Hospital must be intervention sites and will not be randomly allocated to the study group.
- 3) We will seek **approvals**:
 - a. 2 IRB approvals (JHSPH and KEMRI in Kenya) (see section X.E of this document).
 - b. Ministry of Health Approval to work in their sites
 - c. County Approvals (Kisumu and Meru)
 - d. Facility in-charge agreement will be sought at time of provider enrollment.
- 4) A similar three-day **whole-site training** will be carried out in each participating health facility in both study groups on labor management and partograph use by providers following Kenyan and WHO guidelines.

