4	Partograph Extraction tool (revised July 2017)	There are sections where the data extractors will enter the information on the woman and newborn conditions and outcomes that appears a) at the top of the partograph, b) at the bottom of the partograph and c) provider actions recorded on the Jhpiego stamp tool. There are repeatable sections that also allow for data entry on the actual values of the measurements are recorded for 13 parameters (fetal heart rate, cervical dilation, systolic and diastolic blood pressure, amniotic fluid, moulding, head descent, contractions, pulse, temperature, urine protein, acetone and volume). These data will be recorded for each 30 minute interval for the duration of the active stage of labor (4cm dilation to 10cm dilation).
5	Register review tool	This tool will contain the abstracter id, date and facility id, month number of deliveries, Live births (spontaneous, assisted, cesarean, breech), fresh stillbirths, macerated stillbirths, number of twins, early neonatal deaths, number referred, number of maternal deaths
6	Qualitative discussion field guide for ePartogram sites (in-depth interviews or small focus groups)	Qualitative interviews will be conducted with providers in each study arm. In the ePartogram group, qualitative interviews will be administered to better understand the benefits and challenges of ePartogram. Providers will be asked about their experience in using the ePartogram, opinions on various features of the application, and implementation considerations for ePartogram.
7	Qualitative discussion field guide for paper partograph sites (in-depth interviews or small focus groups)	Qualitative interviews will be conducted with providers in the paper partograph group to better understand how providers use the paper partograph in a variety of labor and delivery settings, perceived benefits and challenges in using paper partograph, and the facility conditions that enable or hinder adoption of best practices in labor management

(a) Existing tool already in use

2. Describe the **number and type of study visits and/or contacts** between the study team and the participant, how long they will last, and where/how they will take place.

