
P1. Compliance with globally-recommended labor monitoring practices and recording on the partograph of the information obtained – complete on admission (Tool 4)
	
We will examine each parameter and enter to the database.
 
Overall, this will be marked ‘yes’ if 11 of the 12 items (all except urine volume) are measured at admission (fetal heart rate, cervical dilation, systolic and diastolic blood pressure, amniotic fluid, moulding, head descent, contractions, pulse, temperature, urine protein, acetone and volume); and otherwise ‘no’. Binary variable.
	
All labors with partograph or ePartogram
 
Unit of analysis is each case (partograph).
	
First, we will examine the frequency/prevalence of each measurement recorded on admission and compare between the two study groups
 
Second, We will examine the percent of cases marked ‘yes’ (defined at left). Independent variable is study group. Bivariate analysis will be an unadjusted logistic regression accounting for clustering in the facility or in the provider. In multivariable analysis, other control factors added may be facility type, client volume, region or provider variables.

- Complete over entire labor (Tool 4)
	
We will examine each parameter and enter to the database. Then we will see how many hours was the labor for the appropriate frequency, per the Jhpiego Clinical Rules and determine whether this was done to a large extent on time.
 
Overall, this will be marked ‘yes’ if 11 of the 12 items (all except urine volume) are measured in first 4-hour period at the specified intervals (reviewer will determine for each item if occurred within the interval): fetal heart rate every 30 min, cervical
	
All labors with partograph or ePartogram
	
Same as above – except it will be for the first four hour period

	dilation every 4 hours, systolic and diastolic blood pressure every 4 hours, amniotic fluid if membranes rupture, moulding when present head descent every 2 hours, contractions every 30 min, pulse every 30 min, temperature every 2 hours, urine protein, acetone and volume, all at every 4 hours. ; and otherwise ‘no’. Binary variable.		
- Complete over entire labor for a subset of women who arrived at 4 or 5 cm			

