a. If the study has **different arms**, explain the process for **assigning participants** (intervention/control, case/control), including the sequence and timing of the assignment.

This will be a cluster-randomized trial. See section on randomization under Section III Methods.

b. If human biospecimens (blood, urine, saliva, etc.) will be collected, provide details about who will collect the specimen, the volume (ml) and frequency of collection, how the specimen will be used, stored, identified, and disposed of when the study is over. If specimens will be collected for use in future research (beyond this study), complete the Biospecimen Repository section below. **N/A**

c. If genetic/genomic analyses are planned, address whether the data will be contributed to a GWAS or other large dataset. Address returning unanticipated incidental genetic findings to study participants. **N/A**

d. If clinical or laboratory work will be performed at JHU/JHH, provide the JH Biosafety Registration Number. **N/A**

e. If you will perform investigational or standard diagnostic laboratory tests using human samples or data, clarify whether the tests are validated and/or the lab is certified (for example is CLIA certified in the U.S.). Explain the failure rate and under what circumstances you will repeat a test. For all human testing (biomedical, psychological, educational, etc.), clarify your plans for reporting test results to participants and/or to their families or clinicians. Address returning unanticipated incidental findings to study participants. **N/A**

f. If your study involves medical, pharmaceutical or other therapeutic intervention, provide the following information:

- Will the study staff be **blind** to participant intervention status?

The in-charge and the providers at selected ePartogram sites will know that their site has been selected to use this innovation, so they will not be blinded.

The in-charge and providers at the paper-partograph control sites will not be told officially about the ePartogram being used in other sites, just that their site is part of a partograph training and monitoring intervention. These individuals may find out about the ePartogram being used elsewhere, from contamination/spillover from providers in other sites or from communications with county health officials.

- Will participants receive standard care or have current therapy **stopped**?

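### Cervical dilation at admission is in neither adjustment list, although facilities are assigned purposively and arrival stage could differ by arm

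*Combined protocol and SAP*

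**What the plan says.** **Design.** Section III.A states: "The study design is a quasi-experimental design evaluation with labor management outcomes compared" between intervention and control facilities. Its rule for each region is "equal numbers of facilities that will be purposively assigned to the study groups", with similarity sought on birth volume, staffing and level of emergency obstetric care. One named hospital in each county "must be intervention sites and will not be randomly allocated to the study group". Section V.C.6.a says instead "This will be a cluster-randomized trial" and refers back to Section III, where only the purposive assignment is described.

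**Adjustment.** The statistical analysis plan in Section V.C.4 names possible confounders at three levels. The facility list is open-ended, the provider list has experience and cadre, and the last level reads "Woman-level possible confounders are age and parity". Table 5 says of the P1 model, which is reused for P2 and P3: "In multivariable analysis, other control factors added may be facility type, client volume, region or provider variables". Admission dilation appears in neither place.

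**Data.** Tool 4 in Table 4 extracts 13 parameters, starting "fetal heart rate, cervical dilation, systolic and diastolic blood pressure", at half-hour steps from 4 cm to 10 cm. In Table 5 one P1 outcome scores whether items, dilation among them, were measured at admission (admission P1). A second scores 11 of 12 items against their due intervals in the first four hours (whole-labor P1). A third row reads "Complete over entire labor for a subset of women who arrived at 4 or 5 cm", with no outcome, cases or analysis entered.

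**The concern.** Without random assignment, the arm comparison depends on adjusting for differences between the women the facilities receive. The matching criteria in Section III.A do not include stage of labor on arrival. Section IV says the sites include higher referral-level hospitals in both counties, and Sections II and V describe referral of laboring women between facilities. The hospitals fixed in one arm could therefore receive a different mix of early and late arrivals.

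Arrival stage also bears on what is measured. A woman admitted close to full dilation has few readings due and little time in which to cross the action line or exceed 12 hours. If the mix differs by arm and the model ignores it, part of that difference would be read as an effect of the ePartogram. The 4 or 5 cm row suggests the authors thought arrival stage relevant. However, it covers one outcome and works by setting all other women aside.

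**Working it through.** **1. The plan's own figure.** This point disputes no sample size, but the planned P3 difference is a useful yardstick.
- Inputs (Section III.B, Table 1): 50% versus 80%; 671 births per arm per month; 80% with a partograph; 19% needing action; 6 facilities per arm; ICC 0.15; coefficient of variation 0.90. Alpha and power are not stated; two-sided 0.05 and 80% are assumed.
- Unadjusted n per arm = (1.960 + 0.842)² × (0.25 + 0.16) / 0.30² = 35.8 (plan: 36).
- Cluster size = 671 × 0.80 × 0.19 / 6 = 17.0. Design effect = 1 + (17.0 − 1) × (1 + 0.90²) × 0.15 = 5.34 (plan: 5.3).
- Records per arm = 35.8 × 5.34 / 0.19, about 1,006 unrounded (plan: 1,004). The figure reproduces.
- Standard error of the planned difference = √(0.41 / 36) = 10.7 points.

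**2. Whole-labor P1.** Fetal heart rate, contractions and pulse are due every 30 minutes. Four observed hours give about 8 readings per item; one hour gives about 2. As an illustration for one item, assume each reading is on time independently with probability 0.90 to 0.95:
- all 8 on time: 0.90⁸ = 43% to 0.95⁸ = 66%;
- both of 2 on time: 0.90² = 81% to 0.95² = 90%.

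The gap is 24 to 38 points, here in favor of late arrivals. A busy late admission could equally have fewer readings taken, so the sign is open.

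**3. P2 and P3.** These are rates among labors classed as normal or as complicated. Section I defines prolonged labor by crossing the action line or lasting over 12 hours, and a late arrival has less observed time in which to do either. Arrival mix can therefore change which labors enter each denominator, and the mix of complications in the P3 composite. The documents do not show that arrival dilation changes the rate of appropriate action within a given complication.

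**4. Size.** For a binary late-arrival indicator, the spurious difference between arms is approximately

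bias = (difference between arms in share arriving late) × (difference in outcome between late and early arrivals).

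The documents give neither factor, so both are assumed:

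| Imbalance | Gradient 10 | 20 | 30 | 40 points |
|---|---|---|---|---|
| 5 points | 0.5 | 1.0 | 1.5 | 2.0 |
| 10 points | 1.0 | 2.0 | 3.0 | 4.0 |
| 20 points | 2.0 | 4.0 | 6.0 | 8.0 |

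All values are below the 10.7-point standard error and the 30-point difference planned for P3. No target difference is stated for P1 or P2.

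**5. Missing dilation.** Section II cites a Kenyan survey with all partograph components complete in 58% of cases; there is no figure for dilation alone. For the P3 comparison, the effective number per arm is 1,004 × 0.19 / 5.34 = 35.7, with power of 77% by the pooled-variance test. If 20% of records (assumed) were dropped for missing dilation, 28.6 would remain, with power of 67%. Dropping records would also select on how well the provider recorded, which the ePartogram is meant to change.

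**The case against.** The strongest reply is that the lists are candidates. The plan speaks of possible confounders, says confounding will be evaluated, and says factors may be added. A reader might infer that the models adjust for age and parity alone; that is wrong, since facility and provider factors are also listed. Still, an analyst who followed the lists would not adjust for arrival stage, and the woman-level list, unlike the facility list, is not left open.

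Second, whole-labor P1 partly allows for labor length already. It considers how long the labor lasted, judges each item against its interval, and stops at four hours. This narrows the concern but does not remove it, because the number of readings to be met within four hours still depends on arrival stage. The 4 or 5 cm row may be meant to take its method from the row above; even so, it covers one outcome in a subset.

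Third, a reader might infer that dilation is available for every woman because it is extracted. The documents show only a field. Recording it is itself scored in admission P1, and the ePartogram issues reminders, so missingness may differ by arm. Section II adds that paper partographs are often completed in retrospect. First recorded dilation could therefore be affected by the intervention, and adjustment for it could add bias. This stands, and is why the covariate should be the admission examination reading, with the models shown both ways.

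Fourth, the plan does not say that arrival dilation drives complication risk. That is clinical inference, and the P2 and P3 argument here does not need it.

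**Conclusion.** The omission is real and worth correcting. Assignment is not random, arrival stage is not among the matching criteria, and a baseline variable with a field in the extraction tool is in neither adjustment list. The case is clearest for whole-labor P1. For P2 and P3 it rests mainly on which labors are classed as normal or complicated.

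The size is hypothetical: 0.5 to 8 points over the assumed ranges, with unknown sign. That is small against the 30 points planned for P3, but could matter if the true effect is modest. A reader might infer that the results will be biased toward the ePartogram, or that adjustment would remove the bias. The documents support neither: they give no dilation distribution by arm and no outcome gradient, and the covariate may be missing or recorded differently by arm.

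**What to change.** In Section V.C.4 and Table 5:

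- Prespecify dilation at the admission examination (for example 4–5, 6–7, 8–10 cm) as a woman-level covariate, alongside the listed age and parity, for whole-labor P1 and in the P2 and P3 models.
- Do not use it for admission P1, where it is a scored item, or for S1, which uses counts from the register tool.
- Keep labors with unrecorded dilation in the analysis by a stated missing-data method that allows missingness to differ by arm. Report the number missing in each arm.
- Report each model without dilation alongside.
- Complete the 4 or 5 cm row, and reconcile the design statements in Sections III.A and V.C.6.a.

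The cost is a few lines of plan text and the work of specifying the missing-data method. No new data collection is needed and the sample size is unchanged. The limitation remains that dilation may be missing or recorded differently by arm, so adjustment reduces the bias and cannot be relied on to remove it.
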